6.2 Schedule or Visits and Assessments

For both parts of the trial, all study visits and procedures are detailed in the Schedule of Visits and Assessments tables presented in this section. The detailed description of the study visits and assessments is in sections 6.3 and 6.4. Adherence to the schedule of visits and assessments is required and visits should be planned accordingly.

6.2.1 Part A

Table 6: Schedule of visits and assessments in Part A

Protocol Activities	Screening ¹		Treatment Period ²		End of treatment ³	Follow-up ⁴
	Days -28 to -1	Days -7 to -1	Days 8, 15 and 22			
Informed consent/ Registration ⁵	X					
Demographics, medical history	X					
Physical examination (incl. vital signs)		X		At each visit prior to each CC-486 cycle. Vital signs will be assessed as per site’s standard practice	X	According to SoC
ECOG PS		X		At each visit prior to each CC-486 cycle	X	
Serum pregnancy test ⁶		X		As clinically indicated		
Hematology ⁷		X	X	Within 3 days of every visit prior to each CC-486 cycle and at day 8, day 15 and day 22 of each cycle (± 1 day)	X	
Blood chemistry ⁷		X		Within 3 days of every visit prior to each CC-486 cycle	X	
INR or PT AND aPTT/PTT		X		As clinically indicated		
CA-125 ⁸		X		Within 3 days of every visit prior to each CC-486 cycle	X	X
AEs assessments		X		At each visit prior to each CC-486 cycle	X	X ⁹
Concomitant treatments	X ¹⁰			At each visit prior to each CC-486 cycle	X	X ¹¹
Tumor burden assessments ¹²	X			1 st assessment: 6 weeks (± 1 week) after first CC-486 intake. Then every 12 weeks (± 1 week)		X
FFPE block from debulking surgery (optional) ¹³	X					
Tumor biopsy (mandatory) ¹⁴	X			6 weeks (± 1 week) after first CC-486 intake		
Whole blood for DNA methylation analysis ¹⁵				On Day 1 of the 1 st CC-486 cycle and on the pre-treatment visit prior to the 2 nd CC-486 cycle		

Notes:

- All assessments should be performed within 3 days of the scheduled visit, unless otherwise specified.
- All pre-treatment tests/procedures should be performed and assessed by the Investigator prior to dosing.

Footnotes:

1: Day -1 is the day before subject enrollment (see footnote 5)

2: Study treatment with CC-486 should start within 3 days of enrollment. The first on-treatment visit should occur on Day 1 of the 1st CC-486 cycle (subject should receive the first CC-486 dose during the visit and after the whole blood sample for DNA methylation was drawn). Afterwards, study visits are scheduled every 4 weeks \pm 3 days and should be done during the CC-486 off period as close as possible to restarting the next CC-486 cycle. Additionally, every 21 days (\pm 3 days) subjects will visit the site to receive pembrolizumab. Refer to section 5.3.3 for details on the administration of each schedule. Study treatment will continue until progressive disease according to irRECIST criteria, unacceptable toxicity, consent withdrawal or the Investigator concludes that is in the subject's best interest to discontinue (or any other withdrawal criteria is met according to section 5.5). Progression and study treatment discontinuation should not be declared on the basis of CA-125 alone.

In case there is a need to permanently discontinue one of the study drugs, the other one will also be discontinued and the subjects will undergo the End of treatment visit (and begin the Follow-up phase if applicable as per footnote 4).

3: End of Treatment visit must be scheduled 30 days (\pm 7 days) after the last administration of any study drug. The End of Treatment will be the last study visit for all subjects except those requiring follow-up according to footnote #4.

4: The subjects that will enter the follow-up phase are those who:

- Discontinue treatment for reasons different than irPD. These subjects will continue to be followed up to assess response/progression (with tumor burden assessments and CA-125) every 12 weeks (\pm 1 week) until irPD. After irPD, and provided that subject has undergone the End of Treatment visit, all subjects will be taken off the study unless requiring AE/SAE follow-up according to the next bullet.
- Discontinue treatment for any reason and have ongoing SAEs (regardless of relationship with study drugs) or study treatment-related AEs at time of the End of Treatment visit. Monitoring of these events will continue as clinically indicated until the events have resolved (or return to baseline) or in the Investigator's opinion, are unlikely to resolve due to the nature of the condition and/or the subject's underlying disease. Frequency of visits will be according to Investigator judgment.

5: There is no window to obtain the signed and dated PICF. Study specific screening assessments not considered standard practice by the institution must start only once the PICF has been signed. Registration takes place as soon as the subject signs the PICF. After screening procedures and if subject meets all eligibility criteria, enrollment will be done according to the process described in section 6.1.2.1.

6: Only in women of childbearing potential. Refer to section 4.1 for definition of women of childbearing potential.

7: Hematology: Hemoglobin, Absolute Neutrophils Count (ANC), Platelets. Blood chemistry: creatinine, AST, ALT, alkaline phosphatase, total bilirubin, glucose, TSH. There is no need to repeat hematology and blood chemistry prior to first dose of study treatment provided that they were done at screening within 7 days of enrollment, unless deemed clinically required by the Investigator. During treatment period hematology will be done within 3 days of every visit prior to each CC-486 cycle and on Days 8, 15 and 22 (\pm 1 day). Blood chemistry will be done within 3 days of every visit prior to each CC-486 cycle. There is no need to repeat them prior to pembrolizumab administration unless clinically indicated and/or required according to the standard of care at the

institution.

8: There is no need to repeat CA-125 prior to first dose of study treatment provided that it was done at screening within 7 days of enrollment. Whenever possible, CA-125 should be tested at the same laboratory and with the same technique throughout the study. At the End of Treatment visit and during the follow-up, CA-125 will only be tested in subjects without irPD at time of study treatment discontinuation.

9: During the follow-up phase, only SAEs (regardless of the relationship to study drugs) and non-serious AEs related to study treatments are to be reported and/or followed up (refer to section 6.3.4).

10: Concomitant treatments to be collected from date the PICF is signed

11: Only concomitant treatments to treat AEs related to study treatment and SAEs (regardless of their relationship) will be recorded after the End of Treatment visit

12: CT/MRI of chest abdomen and pelvis to be done at each tumor assessment. The schedule of assessments should be fixed according to the calendar, regardless of treatment interruptions. The first post-baseline assessment will be done 6 weeks (\pm 1 week) after first CC-486 intake. Subsequent assessments should be done thereafter every 12 weeks (\pm 1 week) taking as a reference the date of the first post-baseline tumor assessment. Tumor burden assessments will be done according to irRECIST criteria until documentation of irPD regardless of the end of study treatment and start of subsequent anticancer therapy or CA-125 values. Confirmation of progression (irPD) is recommended minimum 4 weeks after the first irPD assessment and is required during the flare time-window of the first 12 weeks of treatment. If there is suspicion of disease progression based on clinical or laboratory findings before the next scheduled assessment, an unscheduled assessment should be performed at the Investigator's discretion. During the follow-up, tumor assessments will only be required in subjects without irPD at time of End of treatment visit.

13: For subjects consenting to this optional tissue acquisition part of the study, a FFPE block/partial block from the EOC debulking surgery will be obtained (or a minimum of 15 unstained slides in case FFPE tissue block cannot be provided).

14: Image-guided core tumor biopsy is mandatory at baseline (within 28 days of study treatment start) and 6 weeks (\pm 1 week) after first CC-486 intake. The second biopsy must be done during the on-treatment period of the 2nd CC-486 cycle. As much as possible and if clinically indicated, the second biopsy should be scheduled to coincide with the 1st post-baseline tumor burden assessment (both 6 weeks \pm 1 week after first CC-486 intake) so the image-guided biopsy is done at the same time the subject undergoes the scans to assess response/progression. If feasible, a fresh-frozen ascites sample will also be collected in subjects with ascites, during the same procedure as the biopsy. Refer to section 6.4.7.1 and the Study Laboratory Manual for additional details.

15: Whole blood for DNA methylation analysis will be obtained via venipuncture. On day 1 of the 1st CC-486 cycle, sample should be obtained prior to the first CC-486 intake.

6.2.2 Part B

Table 7: Schedule of visits and assessments in Part B

Protocol Activities	Screening ¹		Treatment Period ²	End of treatment ³	Follow-up ⁴
	Days -28 to -1	Days -7 to -1			
Informed consent ⁵	X				
Demographics, medical history	X				
Physical examination (incl. Vital signs)		X	At each visit prior to each CC-486 cycle (Arm A) or each PEM infusion (Arm B). Vital signs will be assessed as per site's standard practice	X	According to SoC
ECOG PS		X	At each visit prior to each CC-486 cycle	X	
Serum pregnancy test ⁶		X	As clinically indicated		
Hematology ⁷		X	Within 3 days of every visit prior to each CC-486 cycle and at day 8, day 15 and day 22 of each cycle (± 1 day) (Arm A) or each PEM infusion (Arm B)	X	
Blood chemistry ⁷		X	Within 3 days of every visit prior to each CC-486 cycle (Arm A) or each PEM infusion (Arm B)	X	
INR or PT AND aPTT/PTT		X	As clinically indicated		
CA-125 ⁸		X	Within 3 days of every visit prior to each CC-486 cycle (Arm A) or each PEM infusion (Arm B)	X	X
AEs assessments		X	At each visit prior to each CC-486 cycle (Arm A) or each PEM infusion (Arm B)	X	X ⁹
Concomitant treatments	X ¹⁰		At each visit prior to each CC-486 cycle (Arm A) or each PEM infusion (Arm B)	X	X ¹¹
Tumor burden assessments ¹²	X		Every 12 weeks (± 1 week)		X
FFPE block from debulking surgery (optional) ¹³	X				
Tumor biopsy (optional) ¹⁴	X		6 weeks (± 1 week) after first dose of study treatment		

Notes:

- All assessments should be performed within 3 days of the scheduled visit, unless otherwise specified.
- All pre-treatment tests/procedures should be performed and assessed by the Investigator prior to dosing.

Footnotes:

1: Day -1 is the day before randomization.

2: Study treatment should start within 3 days of randomization. In Arm A, the first on-treatment visit should occur on Day 1 of the 1st CC-486 cycle (when subject should receive the first CC-486 dose during the visit). Afterwards, study visits are scheduled every 4 weeks \pm 3 days and should be done during the CC-486 off period as close as possible to restarting the next CC-486 cycle. Additionally, every 21 days (\pm 3 days) subjects will visit the site to receive pembrolizumab. In Arm B, study visits are scheduled every 21 days \pm 3 days, prior to each pembrolizumab infusion. Study treatment will continue until progressive disease according to irRECIST criteria, unacceptable toxicity, consent withdrawal or the Investigator concludes that is in the subject's best interest to discontinue (or any other withdrawal criteria is met according to section 5.5). Progression and study treatment discontinuation should not be declared on the basis of CA-125 alone.

In Arm A (CC-486 and pembrolizumab), in case there is a need to permanently discontinue one of the study drugs, the other one will also be discontinued and the subjects will undergo the End of treatment visit and begin the Follow-up phase.

3: End of Treatment visit must be scheduled 30 days (\pm 7 days) after the last administration of any study drug.

4: Once the subject is discontinued from study treatment and has undergone the End of Treatment visit, she will enter in the follow-up phase. Subjects discontinued from study treatment for reasons different than progressive disease per irRECIST (e.g. unacceptable toxicity, physician's decision) will be followed up (with tumor burden assessments and CA-125) every 12 weeks (\pm 1 week) until irPD. Once irPD is declared, all subjects will be followed for survival every 6 months (visit or phone contact) until death or for at least 1 year after the End of Treatment visit, to assess the survival status.

5: There is no window to obtain the signed and dated PICF. Study specific screening assessments not considered standard practice by the institution must start only once the PICF has been obtained. Subject will be registered in the study immediately after PICF signature.

6: Only in women of childbearing potential. Refer to section 4.1 for definition of women of childbearing potential.

7: Hematology: Hemoglobin, Absolute Neutrophils Count (ANC), Platelets. Blood chemistry: creatinine, AST, ALT, alkaline phosphatase, total bilirubin, glucose, TSH. There is no need to repeat hematology and blood chemistry prior to the first dose of study treatment, provided that they were done at screening within 7 days prior to randomization, unless deemed clinically required by the Investigator. During treatment period: In Arm A, hematology will be done within 3 days of every visit prior to each CC-486 cycle and on Days 8, 15 and 22 (\pm 1 day). Blood chemistry will be done within 3 days of every visit prior to each CC-486 cycle. There is no need to repeat them prior to pembrolizumab administration unless clinically indicated and/or required according to the standard of care at the institution. In Arm B, hematology and blood chemistry will be done within 3 days of every visit prior to each pembrolizumab infusion.

8: There is no need to repeat CA-125 prior to first dose of study treatment provided that it was done at screening within 7 days of enrollment. Whenever possible, CA-125 should be tested at the same laboratory and with the same technique throughout the study. At the End of Treatment visit and during the follow-up, CA-125 will only be tested in subjects without irPD at time of study treatment discontinuation.

9: During the follow-up phase, only AEs and SAEs related to study treatments that are ongoing by the End of Treatment visit are to be reported and/or followed up (refer to section 6.3.4).

10: Concomitant treatments to be collected from date the PDCF is signed

11: Only concomitant treatments to treat AEs/SAEs related to study treatment will be recorded after the End of Treatment visit

12: CT/MRI of chest abdomen and pelvis to be done at each tumor burden assessment. The schedule of assessments should be fixed according to the calendar, regardless of treatment interruptions and taking as a reference the randomization date. Tumor burden assessments will be done according to irRECIST criteria until documentation of irPD regardless of the end of study treatment and start of subsequent anticancer therapy or CA-125 values. Confirmation of progression (irPD) is recommended minimum 4 weeks after the first irPD assessment and is required during the flare time-window of the first 12 weeks of treatment. If there is suspicion of disease progression based on clinical or laboratory findings before the next scheduled assessment, an unscheduled assessment should be performed at the Investigator's discretion. During the follow-up, tumor assessments will only be required in subjects without irPD at time of End of treatment visit and only until irPD.

13: For subjects consenting to this optional tissue acquisition part of the study, a FFPE block/partial block from the EOC debulking surgery will be obtained (or a minimum of 15 unstained slides in case FFPE tissue block cannot be provided).

14: Image-guided core tumor biopsy is an optional procedure and will be collected in consenting subjects with lesion amenable to biopsy, at baseline (within 28 days of study treatment start) and 6 weeks (± 1 week) after first dose of study treatment. If feasible, a fresh-frozen ascites sample will also be collected in subjects with ascites, during the same procedure as the biopsy. Refer to section 6.4.7.1 and the Study Laboratory Manual for additional details.

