6.3.2.2 Part B

In Arm A: The first on-treatment visit should occur on Day 1 of the 1st CC-486 cycle (subject should receive the first CC-486 dose during the visit). Afterwards, visits will be done every 4 weeks \pm 3 days, during the CC-486 off period as close as possible to restarting the subsequent CC-486 cycle.

Additionally the subject will visit the clinic at time of each pembrolizumab infusion.

In Arm B: every 21 days \pm 3 days, prior to each pembrolizumab infusion

During the treatment period visits the following assessments will be done in both arms:

- Physical examination (symptom-oriented)
- ECOG PS

- Adverse events assessment
- Concomitant medication
- Laboratory assessments:
 - Hematology: Hemoglobin, Absolute Neutrophils Count (ANC) and Platelets
 - Blood chemistry: creatinine, AST, ALT, alkaline phosphatase, total bilirubin, glucose, TSH
 - Coagulation tests and pregnancy test: only if clinically indicated
 - CA-125
- Tumor burden assessments: if applicable according to sections 6.2 and 6.4.6.1
- Tumor biopsy (optional): if applicable according to sections 6.2 and 6.4.7.1.

Prior to the first dose of study treatment, there is no need to repeat hematology, blood chemistry and CA-125 tests provided they were done at screening within 7 days of randomization, unless deemed clinically required by the Investigator.

In Arm A, prior to each pembrolizumab infusion, there is no need to repeat laboratory tests unless clinically indicated and/or required according to the standard of care at the institution.

In Arm A only, hematology (hemoglobin, Absolute Neutrophils Count (ANC) and platelets) will be repeated at day 8, day 15 and day 22 (± 1 day) of each cycle. No clinical visit is required per protocol on these days. CC-486 dose adjustments, treatment withhold or treatment discontinuation based on hematology test results will be performed as per section 5.7.3.

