6.4.6.1.2 Post-baseline assessments

Post-baseline assessments will be done:

- In Part A:
 - 6 weeks (\pm 1 week) after first CC-486 intake (first post-baseline tumor assessment).
 - Thereafter, every 12 weeks (\pm 1 week), always taking as a reference the date of the first post-baseline tumor assessment (not the date of the immediately previous tumor assessment).
 - Whenever disease progression is suspected based on signs, symptoms, performance status deterioration, CA-125, etc.
 - Confirmation of progression (irPD) is recommended minimum 4 weeks after the first irPD assessment and is required during the flare time-window of the first 12 weeks of treatment.
- In Part B:
 - Every 12 weeks (\pm 1 week), always taking as a reference the date of randomization in the study (not the date of the immediately previous tumor assessment)
 - Whenever disease progression is suspected based on signs, symptoms, performance status deterioration, CA-125, etc.
 - Confirmation of progression (irPD) is recommended minimum 4 weeks after the first irPD assessment and is required during the flare time-window of the first 12 weeks of treatment.

Post baseline assessments will include at least:

- CT or MRI scan of the chest, abdomen, and pelvis (CAP)
- Any other imaging that revealed lesions at baseline
- Any additional imaging as deemed appropriate

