6.4.6.2.1 Evaluation of Response according to CA-125

The GCIG has developed criteria for defining response and progression of ovarian carcinoma based on CA-125.²⁴ The GCIG recommends that for trials of relapsed ovarian cancer the following definition for response according to CA-125 be used.

Definition of response: A response according to CA-125 has occurred if there is at least a 50% reduction in CA-125 levels from a pre-treatment sample. The response must be confirmed and maintained for at least 28 days. Subjects can be evaluated according to CA-125 only if they have a pre-treatment sample that is at least twice the upper limit of normal and within 2 weeks prior to starting treatment (TRIO026 study requires that baseline CA-125 is tested within 7 days prior to enrollment in Part A or randomization in Part B).

To calculate CA-125 responses accurately, the following rules apply:

- Intervening samples and the 28-day confirmatory sample must be less than or equal to (within an assay variability of 10%) the previous sample.
- Variations within the normal range of CA-125 levels will not interfere with the response definition.
- For each subject, it is preferred that the same assay method be used, and the assay must be tested in a quality-control scheme.
- Subjects are not evaluable by CA-125 if they have received mouse antibodies (unless the assay used has been shown not to be influenced by Human anti-mouse antibody) or if there has been medical and/or surgical interference with their peritoneum or pleura during the previous 28 days.

The date when the CA-125 level is first reduced by 50% is the date of the CA-125 response.

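### In Part B, CA-125 is sampled every 4 weeks in Arm A and every 3 weeks in Arm B, so the 28-day confirmation rule can give different CA-125 response rates for identical courses.

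*Protocol*

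**What the plan says.** **Sampling.** Protocol section 6.2.2, Table 7, CA-125 row: "Within 3 days of every visit prior to each CC-486 cycle (Arm A) or each PEM infusion (Arm B". Footnote 2 to that table sets the intervals. In Arm A "study visits are scheduled every 4 weeks", with a window of 3 days either side. "In Arm B, study visits are scheduled every 21 days", with the same window. All four candidate CC-486 schedules have 28-day cycles, so this holds whichever is taken forward.

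**Arm A's other visits.** Section 6.3.2.2: "Additionally the subject will visit the clinic at time of each pembrolizumab infusion". CA-125 is not required at those visits: "In Arm A, prior to each pembrolizumab infusion, there is no need to repeat laboratory tests unless clinically indicated" (or required by local standard of care).

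**Response rule.** Section 6.4.6.2.1: after a fall of at least 50%, "The response must be confirmed and maintained for at least 28 days". It adds: "Intervening samples and the 28-day confirmatory sample must be less than or equal to" the previous sample, with a 10% allowance for assay variability.

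**Use.** CA-125 response is a Part B secondary efficacy endpoint (sections 2.2.2 and 8.5). CA-125 is also one of the listed prompts for an unscheduled scan (section 6.4.6.1.2): "Whenever disease progression is suspected based on signs, symptoms, performance status deterioration, CA-125, etc".

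The SAP covers Part A only, where all cohorts share the 28-day grid. Neither document has a rule for the unequal intervals in Part B.

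**The concern.** The confirmation period equals Arm A's nominal sampling interval but falls between one and two of Arm B's. In Arm A the next sample may be enough. In Arm B the next sample usually comes too early, so two later samples must both pass the 10% condition, and each is a further chance to fail on measurement noise. Against that, an Arm A sample taken one day early also fails the 28-day test, and the next comes four weeks later.

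The schedule can therefore create, hide or reverse a difference in CA-125 response between arms with no difference in the underlying marker. The same asymmetry could slightly shift when CA-125 prompts a scan, which is the only way it could reach the primary endpoint.

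**Working it through.** The plan gives no figure for this point, so none is disputed. For reference, its event count reproduces: 4 × (1.960 + 0.842)² / (ln 0.625)² = 142.1, against the stated 142. Nothing below changes it.

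**1. Gaps between samples.** Assume each visit falls uniformly on a whole day within ±3 days of schedule.
- Arm A: of 7 × 7 = 49 pairs of deviations, 21 give a gap under 28 days. P(gap ≥ 28) = 28/49 = 57%.
- Arm B: the longest gap is 21 + 6 = 27 days, so one later sample is not enough. Two later samples span 42 ± 6 = 36 to 48 days.
- Table 7 also lets the draw fall within 3 days of the visit. Depending on how that window is read, the share of gaps reaching 28 days becomes about 55-56% in Arm A and 2-5% in Arm B.

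**2. Duration alone (no noise, 10% condition ignored).** Share of falls confirmed, by how long the fall lasts, with ±3-day visits:

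| Fall lasts (days) | Arm A | Arm B |
|---|---|---|
| 42 | 25% | 6% |
| 49 | 39% | 33% |
| 56 | 55% | 67% |
| 63 | 68% | 94% |
| 70 | 79% | 100% |

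The direction reverses between 49 and 56 days. On exact dates it does not: Arm A leads (100% vs 67% at 56 days) and the arms are equal from 63 days.

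**3. The 10% condition, flat level, one attempt.** For log-normal noise with log-scale SD s, one later sample passes with probability Φ(ln 1.1 / (s√2)). Two successive passes have correlation -0.5. Arm A = 57% × one-sample + 43% × two-sample; Arm B = two-sample.

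| CV (assumed) | One sample | Two samples (Arm B) | Arm A | Difference |
|---|---|---|---|---|
| 10% | 75% | 52% | 65% | +13 |
| 15% | 67% | 39% | 55% | +16 |
| 20% | 63% | 33% | 50% | +17 |

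**4. Full rule, repeat attempts allowed, identical courses in both arms (simulation, ±3-day visits, CV 10-20%).**
- Flat after the fall: about +2 to +14 points for Arm A. For a 60% fall lasting 112 days, 86% vs 82% at CV 10% and 63% vs 50% at CV 20%. For 168 days, 96% vs 94% and 77% vs 66%.
- Still falling: about -10 to +5 points. With a half-life of 60 days the difference is -2 to +4 at 12 weeks and within 1 point from 16 weeks.
- A separate set of assumed courses, log-scale noise SD 0 to 0.15: +0.2 to +3 points with the windows, +7 to +9 on exact dates.

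**5. irPFS.** The mean wait to the next CA-125 draw is 28/2 = 14 days in Arm A and 21/2 = 10.5 in Arm B, a difference of 3.5 days. A 4-month median is 4 × 30.4375 = 121.75 days, and 121.75 / (121.75 + 3.5) = 0.97. Simulation with no true effect, 12-weekly scans, and a share q of progressions scanned at the next CA-125 draw:

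| q | Apparent HR | Rejects in favour of Arm A (nominal 2.5%) |
|---|---|---|
| 10% | 1.00 | 3.1% |
| 25% | 0.99 | 2.1% |
| 50% | 0.98 | 2.9% |
| 100% | 0.97 | 5.1% |

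Monte Carlo standard error is about 0.4-0.6 points.

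**The case against.** **A reader might infer that the 28-day rule is simply easier to meet in Arm A.** The documents do not support this. Because 28 days is exactly Arm A's nominal gap, about 43% of its gaps fall short under the visit window and confirmation waits until about day 56, against about day 42 in Arm B. Steps 2 and 4 show the sign depends on the course.

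**A reader might quote step 3 as a 13-17 point artefact.** That holds only for a perfectly flat level and a single attempt. Section 6.4.6.2.1 does not limit a subject to one attempt.

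**A reader might say Arm B always needs two later samples.** The draw window in Table 7 can stretch a gap past 28 days. So can the pembrolizumab delays allowed in section 5.7.1, because Arm B's draws follow the infusion.

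**A reader might infer a bias in irPFS towards the combination.** Triggered scans are at the investigator's discretion (Table 7, footnote 12), CA-125 alone cannot declare progression, and scheduled scans are 12-weekly from randomization in both arms. Signs and symptoms also prompt scans, and Arm A has more clinic contacts, which could work the other way. That was not modelled.

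**It may also be said** that this is one of five secondary efficacy endpoints in a phase II study, assessed only in CA-125-evaluable subjects, and that Part B analysis is left to separate documents. That supports a low rating. It does not remove the point: the two nominal grids coincide only every 84 days (3 × 28 = 4 × 21), so an analysis rule cannot recover samples that were not taken on a common schedule.

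**Conclusion.** The unequal sampling is plain in the text, and it interacts with the 28-day and 10% conditions. With identical true courses, the CA-125 response rates can differ by about -10 to +14 percentage points (Arm A minus Arm B). The difference usually favours Arm A when the level is flat after the fall, and is near zero or reversed when it is still falling.

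This rests on assumptions outside the documents: CV 10-20%, uniform ±3-day visits, the shape and length of the fall, and repeat attempts allowed. The range describes those scenarios and is not a bound. The noise-free figures in step 2 for a single fixed duration spread wider (+19 points at 42 days, -26 at 63).

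The effect on irPFS is negligible (HR about 0.97-1.00, the low end only if CA-125 prompted the scan for every progression) and its net direction is uncertain. The documents do not support saying that both consequences favour the combination. Minor severity; a cheap improvement.

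**What to change.** In Table 7 and sections 6.3.2.2 and 6.4.6.2:
- Draw CA-125 for the response endpoint on one 21-day calendar counted from randomization in both arms, taken in Arm A at the nearest infusion visit it already attends.
- State one visit tolerance for the 28-day confirmation, the same in both arms, and say which later sample normally confirms.
- If pre-cycle CA-125 draws are kept in Arm A, leave them out of the response derivation.

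A calendar is better than tying draws to the infusion itself. Arm A's first infusion comes 7 ± 3 days after CC-486 starts (section 5.2), so infusion-linked draws run about a week out of phase with Arm B and move with treatment holds. Using the nearest infusion keeps the spacing equal but leaves some of that offset. Arm A's hematology on days 8, 15 and 22 and before each 28-day cycle is nominally weekly, so every 21-day date also falls on an existing blood draw. That is an option if the offset matters and the same laboratory can be used.

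Cost: 28/21 = 1.33, about one third more CA-125 tests in Arm A, with no extra visits. The 142 events and 150 subjects do not change. Section 3.2 already allows for an amendment before Part B.
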